## 10 ADVERSE EVENTS

### 10.1 Definitions

#### 10.1.1 Adverse Events (AEs)

For the purposes of this study, an AE is any untoward medical occurrence (including a clinically significant abnormal laboratory finding) that occurs in the protocol-specified AE reporting period; the event does not necessarily have a causal relationship with that treatment or usage.

An AE includes medical conditions, signs, and symptoms not previously observed in the subject that emerge during the protocol-specified AE reporting period, including signs or symptoms associated with pre-existing underlying conditions that were not present prior to the AE reporting period.

Adverse events therefore include the following:

- All AEs, whether suspected to be causally related to study drug or otherwise.
- All AEs secondary to any medication overdose, medication error, abuse, withdrawal, sensitivity, or toxicity.
- Illnesses apparently unrelated to study drug, including the worsening of a pre-existing illness (see paragraph below on Pre-existing Conditions).
- Injury or accidents. Note that if a medical condition is known to have caused the injury or accident (eg, a fall secondary to dizziness), the medical condition (dizziness) and the accident (fall) should be reported as 2 separate AEs.
- Abnormalities in physiological testing or physical examination findings that require clinical intervention or further investigation (beyond ordering a repeat [confirmatory] test).
- Laboratory abnormalities that require clinical intervention or further investigation (beyond ordering a repeat [confirmatory] test) unless they are associated with an already reported clinical event. Laboratory abnormalities associated with a clinical event reported as an AE (eg, elevated liver enzymes in a subject with jaundice) should be described under ‘Comments’ on the report of the clinical event rather than reported as separate AEs.

The following guidelines are to be used when reporting AEs for this study:

**Medical Diagnoses** – Whenever possible, a medical diagnosis term should be used to report AEs instead of signs and symptoms due to a common etiology, as determined by qualified medical study staff. For example, pneumonia should be the reported AE term, instead of fever, dyspnea, etc., when the diagnosis has been established. Signs and symptoms should be reported as event terms only when the medical diagnosis remains unknown, and revised to a medical diagnosis term once it has been established.

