- No other reason was identified that explains the increased ALT/AST with or without an increased bilirubin (eg, viral hepatitis, acute liver disease).

If new elevations in ALT or AST > 3 times ULN, with or without an elevation of total serum bilirubin > 2 times ULN are identified, the following steps are to be taken:

- Temporary discontinuation of study medication.
- Repeat testing of ALT, AST, ALP and total bilirubin, to be completed within 48 to 72 hours to confirm the abnormalities and to determine trend.
- Study medication should not be resumed until monitoring indicates abnormalities have resolved, are stable, or are not rapidly increasing.

**Worsening of Anemia** – In this study, it is possible that some subjects may experience a worsening of anemia. Worsening of anemia should not be considered an AE unless the worsening of anemia is associated with a cause other than the subject’s CKD.

**Renal-Related Events** – Some subjects will experience a progression of their CKD during the study as part of the natural course of the disease. In addition, the study population is prone to experience acute, transient loss of kidney function of different etiologies, sometimes concomitantly complicated by progression of CKD.

To ensure consistent reporting of renal events, the following guidelines are to be used when reporting a renal-related AE:

- The following situations **should always be reported as SAEs** with the respective seriousness criteria selected (see [Section 10.1.2](#)):
  - **Progression of CKD leading to chronic dialysis**: Subjects who undergo transition to chronic maintenance dialysis should be reported using the verbatim SAE term of “progression to end-stage renal disease” (ESRD) and the additional seriousness criterion “chronic dialysis”
  - **Any medical event requiring transient acute dialysis**: Subjects who undergo transient acute dialysis should be reported using the verbatim SAE term reflecting the indication for the dialysis. Examples of verbatim AE terms include hyperkalemia, volume overload, acute kidney injury, and uremia. The additional seriousness criterion “acute dialysis” should be selected.
  - **Kidney transplantation**: Subject receiving a kidney transplant should be reported using the verbatim SAE term “Progression to ESRD”, with the additional serious criterion of “kidney transplant” selected.

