- The following situations will be **reported as SAEs if they meet seriousness criteria** (see [Section 10.1.2](#)); otherwise, they should be reported as AEs:
  - **Acute kidney injury not requiring dialysis** – The reported AE term should reflect the etiology for the impairment of the renal function. Non-specific AE terms such as “Decreased eGFR” or “Increased creatinine” should be avoided whenever the underlying etiology is known.
    - Examples of verbatim AE terms for prerenal impairment include hypovolemia, hepatorenal syndrome, and heart failure
    - Examples of verbatim AE terms for intrarenal impairment include acute tubular necrosis, acute interstitial nephritis, and glomerulonephritis
    - Examples of verbatim AE terms for postrenal impairment include hydronephrosis, pelvicaliectasis, and urinary tract obstruction
  - **Progression of CKD not requiring dialysis** – If permanent loss of renal function due to underlying CKD has occurred, the reported AE term should reflect the underlying etiology. Non-specific terms such as “Decreased eGFR,” “Increased creatinine,” or “Worsening CKD” should be avoided whenever the underlying etiology is known. Examples of verbatim AE terms include worsening lupus nephritis, worsening diabetic kidney disease, and worsening glomerulonephritis.
  - **Medical conditions related to CKD that occur without acute kidney injury or progression of CKD** – If there is no decline in kidney function, the medical complication of CKD itself should be reported. AE terms such as “Progression of CKD” or “Acute Kidney Injury,” should be avoided when there is no decline in kidney function. Examples of AE terms include edema and hyperkalemia.

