## **11.7 Safety Analyses**

The reporting of safety data is descriptive, and will include all subjects who receive at least one dose of study medication. The following variables are the safety endpoints: Adverse events, vital signs, ECGs, and laboratory parameters.

AEs will be summarized based on the frequency of AEs and their severity for all treated subjects. Overall safety and tolerability will be assessed with treatment-emergent AEs, laboratory results, and other safety variables including summaries of vital signs and ECGs. As appropriate, summaries may also include change from baseline and shift tables. All AEs will be coded using the Medical Dictionary for Regulatory Activities (MedDRA) and summarized by dose level. Data will be summarized using preferred term and primary system organ class.

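### Prerenal kidney injury not needing dialysis is reported under its cause with no linked term or flag, so it cannot be identified in the adverse event tables by dose

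*Protocol*

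**What the plan says.** The protocol file holds more than one version. The renal reporting guidance appears in the version whose primary analysis is an ANCOVA, and section numbers here refer to that version.

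Section 10.1.1, under Renal-Related Events, notes that this population is liable to sudden, temporary falls in kidney function and sets out how sites should name such events.

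- **Kidney injury without dialysis.** "The reported AE term should reflect the etiology for the impairment of the renal function". Decreased eGFR and increased creatinine are to be avoided as terms when the cause is known. Three sets of examples follow. The first set is the one that matters here: "Examples of verbatim AE terms for prerenal impairment include hypovolemia, hepatorenal syndrome, and heart failure". The second set, where the damage lies within the kidney itself, consists of three kidney diagnoses, among them acute tubular necrosis. The third set, where the cause lies downstream of the kidney, consists of three renal or urinary diagnoses, among them hydronephrosis.
- **Events needing acute dialysis.** These "should be reported using the verbatim SAE term reflecting the indication for the dialysis". The illustrative terms given there range from a metabolic disturbance (hyperkalemia) to the renal diagnosis itself (acute kidney injury). The site must also select an acute-dialysis seriousness criterion.

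Section 11.7 codes adverse events in MedDRA and summarizes them by dose level: "Data will be summarized using preferred term and primary system organ class". The same section makes laboratory parameters a separate safety endpoint and permits change-from-baseline and shift summaries where appropriate. Section 11 leaves the detail of the safety analyses to the SAP, which is not at hand. Appendix A schedules chemistry and eGFR at every visit from screening to Week 18.

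**The concern.** The guidance aims at consistent reporting of renal events. For one type of event it does the reverse. A subject whose kidney function falls because of volume depletion may be recorded as having hypovolemia, and one whose kidney function falls because of cardiac decompensation as having heart failure. Neither term mentions the kidney. Once coded, such a record is identical to one for a subject with the same condition and intact kidney function.

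At stake is the ability to read kidney injury from the adverse event tables of a dose-finding trial in chronic kidney disease. With 12 subjects planned per group, one or two events in an arm make up most of what the table can show.

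This is a matter of data capture, so the SAP cannot settle it. An SAP can group preferred terms in any way it likes, but it cannot split a single preferred term by a fact that was never coded.

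**Working it through.** The protocol states no figure on this point, so there is none to reproduce. The check is a reading of the rule against the tabulation, followed by an illustration on assumed values.

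**Step 1: which cases lose their renal identity.** Section 10.1.1 gives 3 + 3 + 3 = 9 example terms for kidney injury without dialysis.

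- Prerenal: hepatorenal syndrome names the kidney; hypovolemia and heart failure do not.
- Intrarenal: all three are kidney diagnoses.
- Postrenal: all three are renal or urinary diagnoses.

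So 7 of the 9 remain recognizable and 2 do not, both of them prerenal. For dialysis cases, hyperkalemia or volume overload alone would be ambiguous, but acute kidney injury and uremia are also listed and the acute-dialysis criterion marks the record. The affected group is therefore prerenal injury without dialysis.

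**Step 2: whether another adverse event item recovers them.** Injury without dialysis has no counterpart to the acute-dialysis criterion. Section 10.1.1 sends laboratory abnormalities tied to a reported clinical event to the comments on that event. Comments are free text and play no part in a preferred-term summary.

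**Step 3: whether the laboratory data recover them.** In part. On-treatment visits are 14 days apart by schedule. With windows of 3 days either side, consecutive visits can be 14 + 3 + 3 = 20 days apart. An injury that begins and resolves within that interval may leave no trace in scheduled samples.

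**Step 4: illustration.** The protocol gives n = 12 per group. It gives neither the true risk of kidney injury, p, nor the share of cases recorded under a non-renal term, f. Assume p from 5% to 20% and f from 0 to 75%.

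- Expected recognizable cases per arm = 12 × p × (1 − f)
- Chance of at least one recognizable case in an arm = 1 − [1 − p(1 − f)]^12

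| Assumed p | f = 0 | f = 25% | f = 50% | f = 75% |
|---|---|---|---|---|
| 5% | 0.60 cases; 46% | 0.45; 37% | 0.30; 26% | 0.15; 14% |
| 10% | 1.2; 72% | 0.9; 61% | 0.6; 46% | 0.3; 26% |
| 20% | 2.4; 93% | 1.8; 86% | 1.2; 72% | 0.6; 46% |

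For example, at p = 10% and f = 50%, 12 × 0.10 × 0.50 = 0.6 and 1 − 0.95^12 = 46%. The recognizable count falls in direct proportion to f. If every case carried an identifier, the f = 0 column would apply.

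**The case against.** The strongest reply is that the information is not lost. Creatinine and eGFR are held for every subject at every visit, laboratory parameters are a safety endpoint in their own right, comments may describe the renal finding, and the SAP may well specify laboratory summaries. Section 11.7 does not confine the analysis to preferred term and organ class. A hypovolemia record can be set beside that subject's eGFR. Most of this stands, and it is why the point is limited to what the adverse event summaries can show. It does not close the gap, because transient events can fall between samples and comments are not counted.

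A second reply is that naming events by cause is a deliberate convention, in line with the rest of Section 10.1.1, which prefers a diagnosis to its signs. That is fair. A reader might infer an internal contradiction from the instruction that "the medical condition (dizziness) and the accident (fall) should be reported as 2 separate AEs". The text does not support this: that sentence concerns injuries and accidents, and is not a general rule for a condition and its consequence.

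Third, the guidance does not forbid a term such as acute kidney injury due to a named cause. It discourages the words acute kidney injury only where kidney function has not declined. This is true, but the worked examples lead sites to the bare cause.

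Finally, with 12 subjects per group and descriptive safety reporting, adverse event counts could hardly establish a dose trend under any naming rule. This also stands. The aim is to make cases visible, not to power a comparison.

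**Conclusion.** The point holds in narrow form. Under Section 10.1.1, prerenal kidney injury not needing dialysis can be recorded under a term that does not identify it, and the preferred-term and organ-class summaries in Section 11.7 cannot then show it. Regrouping terms in the SAP cannot undo this, and scheduled creatinine and eGFR are only a partial backstop.

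Size: not derivable from the documents, since neither p nor f is stated. The table above shows only how the loss scales over assumed ranges.

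A reader might infer three stronger conclusions that the documents do not support.

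- **That kidney injury by dose is under-counted across the trial.** The effect is confined to the adverse event tables and to one subtype; the laboratory endpoint does not depend on event wording.
- **That the rule favors a dose.** Sites are blinded to treatment assignment and the same rule applies to every arm, so it lowers sensitivity without biasing the comparison by design.
- **That hypovolemia and heart failure counts are inflated.** Those conditions were present as causes, so they are properly counted.

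The randomized comparison with placebo also ends at Week 6. Section 8.2.5 then switches placebo subjects to vadadustat and adjusts doses by response, so counts by dose after that point do not compare randomized fixed-dose groups. This is a worthwhile, inexpensive improvement and not a flaw in the primary analysis.

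**What to change.** In Section 10.1.1, ask sites either to report kidney injury without dialysis as acute kidney injury due to its named cause, coded so that both parts are kept, or to report the injury and its cause as two linked events. Alternatively, leave the naming rule as it is and add one yes/no field to the adverse event form asking whether the event was associated with a decline in kidney function.

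In the safety summaries, add one row by randomized arm for subjects with any such event, showing the randomized period to Week 6 separately from the later dose-adjustment period. A creatinine- or eGFR-based count by arm, with its threshold set before unblinding, would sit well beside it; that belongs in the SAP and may already be there.

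Cost: one sentence of guidance with either one form field or a second coded term per affected event, and one table row. No new visits or samples are needed. The small downside is the extra data entry and, if linked terms are used, two coded terms for one clinical episode, so the summary should count subjects and not events.

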### **10.1.2 Serious Adverse Events (SAEs)**

Each AE must be classified by the investigator as SERIOUS or NONSERIOUS. An AE that meets 1 or more of the following criteria or outcomes is classified as serious:

- Death
- Life-threatening (see paragraph below on Life-threatening)
- In-patient hospitalization or prolongation of existing hospitalization (see paragraph below on Hospitalization)
- Persistent or significant disability/incapacity (see paragraph below on Disability)
- Congenital anomaly/birth defect
- Is considered a medically important event not meeting the above criteria, but which may jeopardize a subject, or may require medical or surgical intervention to prevent one of the criteria listed in this definition. The following events are considered medically important events for this patient population:
  - Chronic dialysis
  - Acute dialysis
  - Kidney transplantation

Serious also includes any other event that the investigator or sponsor judges to be serious. If there is any doubt whether the information constitutes an AE or SAE, the information is to be treated as an SAE.

**Life-threatening** – Any event in which the subject was at risk of death at the time of the event; ‘life-threatening’ does not refer to an event which hypothetically might have caused death if it were more severe.

**Hospitalization** – Hospitalization is defined as an overnight admission with observation of a minimum of 24 hours. A hospitalization planned before the start of the study for a pre-existing condition that has not worsened during the AE reporting period does not constitute an SAE.

**Disability** – Defined as a substantial disruption in a person’s ability to conduct normal life functions.

### **10.2 Eliciting Adverse Event Information**

The investigator is to report all directly observed AEs and all AEs spontaneously reported by the study subject. In addition, each study subject will be questioned about AEs at each visit following the initiation of treatment.

### **10.3 Reporting**

Each AE is to be classified by the investigator as SERIOUS or NONSERIOUS.

All AEs that occur in study subjects during the AE reporting period specified in the protocol must be reported, whether or not the event is considered related to study medication.

### **10.3.1 Reporting Period**

The AE reporting period for a subject begins upon receiving the first dose of study medication and ends at the final protocol-required visit. In addition, SAEs that occur after the protocol-defined AE reporting period that are considered to be related to the study medication should be recorded and reported to the sponsor's medical monitor or CRO designee.

### **10.3.2 Reporting AEs**

NONSERIOUS AEs are to be reported on the AE CRFs.

### **10.3.3 Reporting SAEs**

Any SAE, regardless of causal relationship, must be reported to the sponsor's medical monitor/medical director or CRO designee **within 24 hours** after the investigator becomes aware of the SAE. Compliance with this time requirement is essential so that the sponsor may comply with its regulatory obligations.

The initial SAE report should be completed as fully as possible but should contain, at a minimum:

- Subject number/ID, sex, and age/date of birth
- The date of report
- Name of the reporter
- Description of the event, including event term(s), seriousness criteria, and a clinical summary of the event
- Causality assessment

Information about all SAEs (either initial or follow-up information) should be collected and recorded in English on the SAE Report Form. The investigator must assess the relationship to each specific component of the study treatment. If the event meets serious criteria, SAE Report Form should be sent to the CRO via email or fax, or the investigator should call the CRO SAE hotline within 24 hours of being made aware of the SAE (reference the site manual for contact information).

The investigator must report follow-up information relating to an SAE to the sponsor's medical monitor/medical director or CRO designee within 24 hours of awareness by submitting a new SAE Report Form. The subject should be observed and monitored carefully until the condition resolves or stabilizes.

All deaths are to be thoroughly investigated and reported. Autopsy reports are to be obtained, if possible, and sent to the CRO via email or fax.

The sponsor and/or its designee are responsible for reporting SAEs to all applicable regulatory agencies and the central ethics committees within the required timeline.

The investigators are responsible for submitting required safety information to their local Institutional Review Board (IRB) or Independent Ethics Committee (IEC) per local regulations. This information includes but is not limited to, any safety alert letter received from the sponsor and any SAEs occurring at their investigative site.

#### 10.3.4 Relationship to Study Medication

The causal relationship of the AE to study medication will be assessed by both the investigator and the sponsor.

The assessment of causal relationship to study drug should be **evidence-based**, and not based on the premise that all AEs are possibly causally related to study drug until proven otherwise.

Examples of evidence that would suggest a causal relationship between the drug and the AE include the occurrence of an AE that is uncommon and known to be strongly associated with drug exposure (eg, angioedema, hepatic injury, Stevens-Johnson Syndrome), or an AE that is uncommon in the population exposed to the drug.

The causal relationship of the AE is assessed using a binary system, and AEs are classified as either ‘related’ or ‘unrelated’:

**Related:** There is ‘reasonable possibility’ that the drug caused the AE. The AE follows a reasonable temporal sequence from the time of drug administration. There is supportive evidence (facts) to suggest a possible causal relationship, irrespective of the degree of certainty between the observed AE and the drug.

**Unrelated:** An AE does not follow a reasonable temporal sequence from administration of the product and/or there is no reasonable possibility that the drug caused the AE. This assessment includes situations where the AE is related to other factors such as the subject’s clinical state, other therapeutic interventions, or concomitant drugs administered to the subject.

Default assessments using the ‘related’ category without supportive evidence for a causal relationship to study drug is generally uninformative and does not contribute meaningfully to the development of the safety profile of the drug or to subject protection.

Investigators are encouraged to choose the most plausible cause for the event(s) from the following list: Medical history, lack of efficacy/worsening of treated condition, study treatment, other treatment (concomitant, or previous), withdrawal of study treatment, administration error, protocol-related procedure, others (specify).

#### 10.3.5 Severity

The investigator will assess each AE as either MILD, MODERATE, or SEVERE using the following guidelines to describe the maximum severity of the AE:

- **MILD:** Does not interfere with subject's usual function.
- **MODERATE:** Interferes to some extent with subject's usual function
- **SEVERE:** Interferes significantly with subject's usual function.

Note that a **severe** AE is not necessarily a **serious** AE. For example, a headache may be severe in intensity, but would not be classified as serious unless it met 1 of the criteria for serious events listed above.

